Risk Title: COVID-19	Risk Description: In view of the negligible risk of systemic adverse effects and/or drug-drug interactions, the risk of experiencing an aggravation of COVID-19 or experiencing interactions with COVID-19 vaccination is considered negligible in this trial. Consequently, subjects who have not been diagnosed with COVID-19 and do not have symptoms suggestive of COVID-19 can safely be enrolled in the trial despite the ongoing pandemic and can follow COVID-19 vaccination programs. Subjects who have been diagnosed with or have symptoms suggestive of COVID-19 carry a significant risk of transmitting the disease to other trial participants and trial staff.
	Risk Mitigation: All subjects will be asked to inform the site immediately (via phone – NOT in person!) if they are diagnosed with or have symptoms suggestive of COVID-19 and they will not be randomized (see exclusion criterion 10.d) and will not be allowed to attend trial visits until local COVID-19 regulations allow it. Subjects who are diagnosed with COVID-19 after randomization may subsequently be asked to complete trial visits (to the extent possible) via phone until applicable negative test results can be provided (if necessary, additional trial supplies may be shipped to the subject) or be withdrawn from the trial at the investigator's discretion (see Section 5.4, Withdrawal from trial and discontinuation of treatment). COVID-19 diagnosis and/or COVID-19 vaccinations should be reported in the eCRF (as AEs or Concomitant therapies, respectively) to enable evaluation of any impacts on the safety of trial subjects or the integrity of trial data.

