5.4 Withdrawal from trial and discontinuation of treatment

In accordance with legal requirements and International Council for Harmonisation (ICH) – Good Clinical Practice (GCP) guidelines, every subject has the right to refuse further participation in this trial (withdrawal from trial) or refuse further treatment (discontinuation of treatment) at any time and without providing reasons. A subject's refusal should be effectuated immediately upon his/her request.

In addition, a subject may be withdrawn from the trial or be discontinued from treatment at any time at the discretion of the investigator.

Reasons for withdrawal from trial or discontinuation of treatment include (but are not necessarily limited to) progressive disease, AE, pregnancy, death, protocol violation, and lost to follow-up. If the IMP application is discontinued regardless of the reason for discontinuation, the subject should be encouraged to continue in the trial.

The reasons for trial withdrawal or treatment discontinuation are to be fully documented on the electronic case report form (eCRF) and an EoT visit should be completed as soon as possible to the extent possible. Subjects who withdraw from trial before randomization will be considered screen failures. In case of treatment discontinuation, the subject should be encouraged to attend remaining trial visits in line with the schedule of assessments (SoA). If a subject is withdrawn from the trial due to an AE or treatment is discontinued due to an AE, the AE must be followed up as outlined in Section 7.12.2.

If subjects are diagnosed with or have symptoms suggestive of COVID-19 they may not be allowed to attend trial visits until local regulations allow it. Subjects who are diagnosed with COVID-19 after randomization may subsequently be asked to complete trial visits (to the extent possible) via phone until applicable negative test results can be provided (if necessary, additional trial supplies may be shipped to the subject) or be withdrawn from the trial at the discretion of the investigator.

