7.13 COVID-19 Considerations

COVID-19 control measures in different countries may impact the ability to adhere to some of the trial procedures described in this protocol. Due to challenges that include, but are not limited to, subject preferences, site closures, travel restrictions, and quarantines, some modifications to trial conduct during the COVID-19 pandemic may be necessary to ensure trial continuity. The following are allowable, as necessary, modifications to trial conduct during the COVID-19 pandemic.

- Prior to a trial visit at the site, the subject may be contacted and may be asked to be screened for potential exposure or infection to COVID-19 per local requirements. If the subject is suspected or known to be infected with COVID-19, the on-site visit may either be re-scheduled or a virtual visit may be performed instead, as applicable.
- If a subject cannot attend the regularly scheduled trial visits in person due to COVID-19 necessitating a limit on in-person contact, the investigator may perform safety and efficacy assessments by phone or video to the extent possible. The investigator may use technology platforms that are considered suitable by the site.
- Source documentation and the eCRF should note that the visit was performed virtually (not face-to-face). If certain trial procedures or assessments cannot be completed per the SoA, the reason for the missed assessment must be noted in the source documentation (e.g., COVID-19) and captured in the protocol deviations documentation.

A detailed assessment of COVID-19-related risk and mitigation measures will be documented in the appropriate trial plans, e.g., trial risk management plan.

Subjects who missed significant WI-NRS assessments due to COVID-19 may be replaced if the total number exceeds 10% of subjects enrolled.

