8.8.1 Primary endpoint

The primary endpoint, mean change in weekly mean WI-NRS recorded in the subject's diary from Baseline to Week 12 for MC2-25 cream compared to MC2-25 vehicle, will be analysed by a mixed model of repeated measures with Baseline weekly mean WI-NRS as covariate and treatment, CKD stage stratum at baseline, systemic CKP-aP treatment status at baseline and visit as fixed factors with a two-sided α =0.05. The weekly mean WI-NRS is calculated as the average of minimum 4 WI-NRS values recorded once daily in the subject's diary from 7 days prior to and including the visit days (i.e., must be recorded for 8 days total).

On the FAS, the primary analysis and one sensitivity analysis will follow a treatment policy strategy irrespective of any potential intercurrent events. On primary analysis, missing values will be replaced following a multiple imputation procedure adequate for the endpoint assuming missingness appearing at random and based on 20 imputations. On the FAS, sensitivity analyses will include imputation by last observation carried forward (LOCF; treatment policy strategy) and multiple imputation of missing data and all data after start of rescue medication (hypothetical strategy).

Applying the same statistical model, further estimands include multiple imputation on the MFAS and as observed on the PPS, both following a treatment policy strategy. If deaths occur, further estimands may be defined following a composite endpoint strategy.

Supportive subgroup analyses will be conducted by dialysis status and CKD stages and by country on the FAS.

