5.2.4 COVID-19 Impacted Visits

Since the primary and secondary efficacy endpoints are derived from the subjects' diaries and summaries of other efficacy endpoints and safety endpoints are as observed, there will be no adjustments made for coronavirus disease of 2019 (COVID-19) impacted visits.

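### Investigator-led withdrawal from the trial ends home-diary collection that could continue, so Week 12 WI-NRS is imputed in an analysis declared treatment policy

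*Protocol*

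**What the plan says.** **Withdrawal.** Protocol Table 1 (COVID-19 row) offers phone visits to a subject diagnosed after randomisation, "or be withdrawn from the trial at the investigator's discretion". Section 5.4 has the same option for COVID-19 ("or be withdrawn from the trial at the discretion of the investigator") and a general clause: "a subject may be withdrawn from the trial or be discontinued from treatment at any time at the discretion of the investigator". One list of reasons serves both decisions: "Reasons for withdrawal from trial or discontinuation of treatment include (but are not necessarily limited to) progressive disease, AE, pregnancy, death, protocol violation", with loss to follow-up also named.

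**Retention.** Section 5.4 encourages the subject to stay in the trial and attend the remaining visits, but only where the IMP has been stopped. A subject who leaves the trial is due one end-of-treatment (EoT) visit (Section 5.4; footnote 3 of the visit schedule).

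**Outcome.** Section 7.9.1 has the subject record WI-NRS once daily in a diary on the 8 days up to and including each on-site visit.

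**Analysis.** Protocol 8.8.1 states that the primary analysis "will follow a treatment policy strategy irrespective of any potential intercurrent events", with multiple imputation under missing at random. SAP 5.2.1 treats fields left empty after dropout as missing, whatever the reason. On COVID-19, SAP 5.2.4 says that "there will be no adjustments made for coronavirus disease of 2019 (COVID-19) impacted visits", because the primary and secondary endpoints come from diaries. Protocol 7.13 adds: "Subjects who missed significant WI-NRS assessments due to COVID-19 may be replaced if the total number exceeds 10% of subjects enrolled".

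**The concern.** A treatment-policy analysis asks what happened to subjects by Week 12 whatever occurred on the way, so it depends on collecting outcomes after the event. A home diary makes that easy: it needs neither attendance nor continued use of the cream. The protocol uses this advantage when treatment stops but not when the investigator ends participation.

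Two things are at stake. Values that could have been observed are replaced by model predictions. The imputation variables in SAP 5.2.1 include neither treatment discontinuation nor reason for withdrawal, so the prediction for a withdrawn cream subject leans on cream subjects who stayed. The sample size also budgets for 10% dropout and little more. SAP 5.2.4's reason for making no COVID-19 adjustment holds for a missed clinic visit, but not for a subject who is out of the trial and keeps no diary. Replacement under Section 7.13 does not recover the original subject's data, and that subject stays in the FAS.

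**Working it through.** **1. Does the EoT visit supply Week 12?** SAP 5.1 assigns an early withdrawal's EoT efficacy data to the nearest scheduled time point. SAP Table 10 gives Week 12 the window Days 72 to 92. An EoT visit before Day 72 falls in an earlier window, so Week 12 stays missing and is imputed. An EoT visit from Day 72 can supply Week 12, provided at least 4 of the 8 diary days are filled (SAP 3.1).

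**2. The plan's sample size.** Inputs from protocol 8.2: d = 1.5, s = 2.46, two-sided 5%, 80% power, 2:1 allocation, 10% dropout.

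- Vehicle n = (1.960 + 0.842)² × 2.46² × (1 + 1/2) / 1.5² = 31.7, rounded up to 32. With 64 on cream the total is 96.
- 96 / 0.90 = 106.7, so 107, against the stated 108. The plan's figure reproduces.

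**3. Power at different losses.** SE = 2.46 × √(1/n₁ + 1/n₂), noncentrality = 1.5 / SE, two-sided t-test. These are unadjusted figures that count only subjects with Week 12 data.

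| Loss | Cream / vehicle | Power |
|---|---|---|
| 0% | 72 / 36 | 84.1% |
| 5% | 68 / 34 | 82.0% |
| 10%, exact | 64.8 / 32.4 | 80.1% |
| 10%, whole subjects | 65 / 32 | 79.8% |
| 15% | 61 / 31 | 78.1% |
| 20% | 58 / 29 | 75.5% |

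The 10% row is the plan's own allowance. The other losses are scenarios, not document figures.

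**4. Possible bias (assumptions, not document figures).** Let w be the share of the cream arm withdrawn with Week 12 imputed, and b the difference from vehicle that those subjects would truly have at Week 12. If imputation credits them with the full 1.5, the overstatement is w × (1.5 − b).

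- Benefit persists, b = 1.5: overstatement 0 at any w.
- Benefit fully lost, b = 0: 0.05 × 1.5 = 0.075 at 5%, and 0.10 × 1.5 = 0.15 at 10%.

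For scale, the standard error with everyone observed is 2.46 × √(1/72 + 1/36) = 0.50. The upper values are therefore 0.15 and 0.30 of a standard error.

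**5. Consistency within Section 5.** Section 5.1 keeps subjects in the trial when an eligibility deviation is found after randomisation, unless safety requires the IMP to stop. Section 5.4 lists protocol violation among the reasons for withdrawal or discontinuation. The two passages need reconciling.

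**The case against.** The strongest reply is that much of this is already handled. Section 5.4 distinguishes leaving the trial from stopping treatment and encourages retention after the latter. Section 5.1 retains subjects with eligibility deviations. Section 6.7.2 does not automatically stop the IMP when a prohibited therapy is used. Phone or virtual visits and shipped supplies are alternatives for COVID-19. A full set of Week 12 assessments is due at withdrawal. All this stands and limits how often the problem arises. It does not reach a subject whom the investigator withdraws before Day 72.

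A reader might infer more than the documents support:

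- **That the plan contradicts its own estimand.** It does not. Treatment policy governs intercurrent events such as stopping the IMP. Leaving the trial creates missing data, which the SAP acknowledges and imputes. The weakness is that some of this missingness is avoidable.
- **That investigators will remove subjects whose itch worsens.** The list of reasons is joint with treatment discontinuation and includes death. It does not say which decision follows from which reason, so dependence on outcome is plausible but not shown.
- **That SAP 5.2.4 leaves COVID-19 losses unhandled.** Missing diary data still go to multiple imputation; only a COVID-specific adjustment is declined.
- **That the power claim fails.** It holds at exactly 10% loss; 79.8% arises from rounding to whole subjects. The planned model also adjusts for baseline and uses earlier visits of withdrawn subjects. With an assumed covariate correlation of 0.3, power is about 83% at 65/32 and 79% at 58/29.

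It would also go too far to allow participation to end only on withdrawn consent, loss to follow-up or death. That would override the discretion for unacceptable adverse events in Table 1.

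**Conclusion.** The point holds in a limited form. Protocol Table 1 and Section 5.4 permit investigator-led withdrawal from the trial without any request to continue the diary, so some obtainable Week 12 values would be imputed under missing at random in a treatment-policy analysis.

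The size is unknown because no rate of such withdrawals is given. If 5% to 10% of the cream arm were affected, the overstatement would run from 0 to 0.075–0.15 points, depending wholly on how much benefit persists off treatment. Power of at least 80% just holds at the budgeted 10% loss, and further loss would reduce it, less so under the adjusted model. In an exploratory phase 2 trial this is a worthwhile inexpensive improvement, not a flaw that undermines the primary analysis.

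**What to change.** In Table 1 and Section 5.4, extend the existing retention wording to any investigator-led withdrawal, COVID-19 included. A subject who has not withdrawn consent would be asked to continue the WI-NRS diary and phone contacts to Week 12. State in SAP 5.2.1 that these values enter the treatment-policy analysis as observed data. Make clear that SAP 5.2.2, which disregards available data for some subjects who discontinue, does not apply to that analysis.

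Reconcile protocol violation as a listed reason in Section 5.4 with Section 5.1. The investigator's discretion over treatment, safety and clinical care, and the subject's right to leave, stay unchanged; the change concerns outcome collection only.

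The cost is a wording amendment, a short SAP clarification, and modest site effort to supply and collect diaries for a few subjects.

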3.0 TRIAL OBJECTIVES AND PURPOSE

The primary objective is to explore the clinical efficacy of MC2-25 cream compared to MC2-25 vehicle in adults with chronic kidney disease-associated pruritus (CKD-aP).

The secondary objectives are to explore the safety of MC2-25 cream compared to MC2-25 vehicle in adults with CKD-aP and other objectives are to explore the subclinical effects of MC2-25 cream in adults with CKD-aP.

4.0 TRIAL DESIGN

4.1 Overall trial design

This is a multicentre, phase 2, randomized, double-blind, 2-arm, parallel-group and vehiclecontrolled trial in subjects with CKD-aP. Approximately 108 eligible subjects will be randomised in a 2:1 ratio to MC-25 cream or MC2-25 vehicle, respectively. Subjects will apply the assigned IMP twice daily for 12 weeks.

The overall trial duration for each subject is maximum 18 weeks. Subjects will be seen at the trial sites at Screening, Baseline, Week 1, Week 4, Week 8, and Week 12 (end of treatment, EoT). Subjects who have ongoing serious adverse events (SAEs) or related adverse events (AEs) at Week 12 will have a follow-up visit at Week 14 or (in case of early treatment discontinuation) 14 days after the EoT visit, whichever comes first. Additionally, phone contacts are planned at Week 2, Week 6, and Week 10.

Figure 1: MC2-25-C1 Clinical Trial Design

4.2 Trial endpoints

Primary Objective:	Primary Endpoint:
To explore the clinical efficacy of MC2-25 cream compared to MC2-25 vehicle in adults with CKD-aP	 Mean change in weekly mean Worst Itch Numeric Rating Score (WI-NRS) recorded in the subject's diary from Baseline to Week 12 for MC2-25 cream compared to MC2-25 vehicle. (Weekly mean WI-NRS is calculated as the average of WI-NRS values recorded in the subject's diary 7 days prior to and including the visits.)
	Secondary Endpoints:
	 Percentage of subjects obtaining a ≥4-point improvement in weekly mean WI-NRS recorded in the subject's diary from Baseline to Week 12 for MC2-25 cream compared to MC2-25 vehicle.
	• Percentage of subjects obtaining a ≥3-point improvement in weekly mean WI-NRS recorded in the subject's diary from Baseline to Week 12 for MC2-25 cream compared to MC2-25 vehicle.
	 Percentage of subjects obtaining a complete response in weekly mean WI-NRS recorded in the subject's diary from Baseline to Week 12 for MC2-25 cream compared to MC2-25 vehicle. (Complete response is defined as scores equal to 0 or 1 in ≥80% of the non-missing WI-NRS values recorded in the subject's diary 7 days prior to and including the visits.)
	Other Endpoints:
	• Mean change in WI-NRS recorded during on-site visits from Baseline to Week 12 for MC2-25 cream compared to MC2-25 vehicle.
	• Mean change in Sleeploss due to Itch Numeric Rating Score (SI-NRS) from Baseline to Week 12 for MC2-25 cream compared to MC2-25 vehicle.
	• Mean change in Skin Dryness Numeric Rating Score (SD-NRS) from Baseline to Week 12 for MC2-25 cream compared to MC2-25 vehicle.

	 Percentage of subjects who reported "Much better" or "A little better" in Subject's Global Impression of Change (SGIC) for Worst Itch (WI), Sleeploss due to Itch (SI), or Skin Dryness (SD) from Baseline to Week 12 for MC2-25 cream compared to MC2-25 vehicle.
	• Percentage of subjects who reported an important improvement in SGIC for WI, SI, or SD at Week 12 for MC2-25 cream compared to MC2-25 vehicle.
	• Change in treatment area size from Baseline to Week 12 for MC2-25 cream compared to MC2-25 vehicle.
	• Change in 5D-Itch from Baseline to Week 12 for MC2-25 cream compared to MC2-25 vehicle.
	• Change in Skindex-10 from Baseline to Week 12 for MC2-25 cream compared to MC2-25 vehicle.
	• Change in EQ-5D-5L from Baseline to Week 12 for MC2-25 cream compared to MC2-25 vehicle.
	• Percentage of subjects obtaining a ≥2-step improvement in Clinician's Global Assessment (CGA) of skin appearance from Baseline to Week 12 for MC2-25 cream compared to MC2-25 vehicle.
	• Percentage of subjects obtaining a ≥2-step improvement in one or more individual signs or in the Clinician's Targeted Assessment (CTA) of skin appearance from Baseline to Week 12 for MC2-25 cream compared to MC2-25 vehicle.
Secondary Objective:	Other Endpoints:
To explore the safety of MC2-25 cream compared to MC2-25 vehicle in adults with CKD-aP	• Frequencies of treatment-emergent adverse events (TEAEs), serious adverse events (SAEs), adverse drug reactions (ADRs), AEs leading to treatment discontinuation or trial withdrawal, and deaths during the trial for MC2-25 cream compared to MC2-25 vehicle.
	• Changes in mean safety assessments: vital signs (heart rate, systolic blood pressure, diastolic blood pressure, temperature) and blood samples (biochemistry,

	 haematology) from Baseline to Week 12 for MC2-25 cream compared to MC2-25 vehicle. Frequency of clinically significant abnormal physical examinations and ECGs from Baseline to Week 12 for MC2-25 cream compared to MC2-25 vehicle. Percentage of subjects who missed 1 or more dialysis visits during the Double-blind Treatment Period.
Other Objective:	Other Endpoints:
To explore the subclinical effects of MC2-25 cream compared to MC2-25 vehicle in adults with CKD-aP	 Changes in biomarkers in skin tape stripping samples from Baseline to Week 12 for MC2-25 cream compared to MC2-25 vehicle. Changes in biomarkers in skin punch biopsy samples from Baseline to Week 12 for MC2-25 cream compared to MC2-25 vehicle.

5.0 SELECTION OF TRIAL POPULATION

5.1 Subject population

The trial population is males or non-pregnant females at least 18 years of age who have chronic kidney disease (CKD) stages G3-G5 (estimated glomerular filtration rate [eGFR] <60 mL/min/1.73 m²) and at least moderate CKD-aP (as defined in inclusion criterion 6). Both subjects on dialysis haemodialysis or haemodiafiltration and not on dialysis will be enrolled (=randomized).

Subjects who fail screening because they do not meet minimum WI-NRS criteria cannot be re-screened. Subjects who fail screening for other reasons may be re-screened once. Reason(s) for screen failure will be recorded in the eCRF. Subjects fulfilling all inclusion and none of the exclusion criteria can be randomized in the trial. Pre-randomization approval of deviations to inclusion or exclusion criteria is not permitted. If deviations to inclusion or exclusion criteria are identified post-randomization, subjects shall continue in the trial as planned unless discontinuation of IMP treatment is warranted for safety reasons.

5.2 Inclusion criteria

Subjects must meet all of the following criteria to be eligible for participation in the trial:

- 1. Adult males or non-pregnant females of any race or ethnicity who are ≥ 18 years of age at the time of screening
- 2. Able to understand the trial and willing to comply with trial requirements
- 3. Has provided written informed consent
- 4. Chronic (>3 months) kidney disease (CKD) stages G3-G5 (i.e., estimated glomerular filtration rate [eGFR] by CKD-EPI creatinine 2021 equation <60 mL/min/1.73 m²)
- 5. Specifically for CKD subjects on haemodialysis (HD) or haemodiafiltration (HDF):
 - Subjects must be established on HD or HDF 3 times per week continuously for at least 3 months prior to the start of screening (Note: at least the 2 last weeks of the 3-month period must have been in-centre dialysis) and must not have plans to change from HD to HDF or vice versa during the trial.
 - b. Subjects who require an occasional additional HD or HDF treatment to manage fluid overload may be enrolled as long as it is anticipated that no more than 4 such treatments will be required in any given month.
- At least moderate CKD-aP defined as WI-NRS ≥4 (i.e., the average of all and at least 4 non-missing scores reported by the subject in the diary for 7 days prior to and including the Baseline day, 8 days in total)
- 7. Female subjects must be of either:
 - Non-childbearing potential, i.e., postmenopausal* or confirmed sterile (e.g., hysterectomy, bilateral salpingectomy or bilateral oophorectomy).
 (*Note: a postmenopausal state is defined as no menses for 12 months without an alternative medical cause. A high follicle stimulating hormone (FSH) level in the postmenopausal range may be used to confirm a postmenopausal state in women not using hormonal contraception or hormonal replacement therapy. However in the absence of 12 months of amenorrhea, a single FSH measurement is insufficient) or,
 - Childbearing potential with a negative highly sensitive urine pregnancy test at the Baseline visit or (in the case of anuria) a negative serum pregnancy test at the Baseline visit that is no more than 3 days old.
- 8. Female subjects of childbearing potential must agree to use a highly effective method of contraception (i.e., a method with a failure rate of less than 1% per year when used consistently and correctly) while receiving double-blind treatment. Highly effective contraception is defined as follows:

- combined (estrogen and progestogen-containing) hormonal contraception associated with inhibition of ovulation: oral, intravaginal, transdermal
- progestogen-only hormonal contraception associated with inhibition of ovulation: oral, injectable, implantable
- intrauterine device (IUD)
- intrauterine hormone-releasing system (IUS)
- bilateral tubal occlusion
- vasectomised partner (provided that is the sole sexual partner of the subject and that the vasectomised partner has received medical assessment of the surgical success)
- sexual abstinence if in line with the preferred and usual lifestyle of the subject and defined as refraining from heterosexual intercourse during the entire period of the trial. Periodic methods of abstinence (e.g., calendar, ovulation, symptothermal, post-ovulation methods) are not accepted methods of contraception.

